8 STUDY ASSESSMENTS AND PROCEDURES

8.1 OUTCOME ASSESSMENTS

Collecting effectiveness outcome data will be centralized; research staff at the Study Coordinating Center will collect the data from patients and surrogates by phone. Telephone-based collection minimizes participants' travel burden. Centralized data collection maintains data collectors being blind to group assignment. The preparedness outcomes will be assessed at 2 weeks post-intervention, as in our R21 trial.¹⁸ We expect roughly 40% of study patients (~160) to die by the 9-month follow-up; deaths are readily identifiable through dialysis clinics and will trigger post-bereavement surveys with surrogates at 3 months and staggered CMS data collection. Post-bereavement assessment at 3 months is based on our efficacy data showing that distress symptoms sharply rose in both groups 2-weeks post-bereavement and then stabilized at 3 months.

Effectiveness Outcomes

Preparedness for end-of-life decision making (measured at baseline and 2 wks post-Session II):

- **Dyad congruence** will be assessed using the Goals-of-Care Tool,^{18,20} which includes two scenarios describing medical conditions commonly occurring in ESRD patients. In the first, the patient develops a severe complication and cannot speak for himself/herself; the medical team believed recovery unlikely and continuing life-sustaining treatment, including dialysis, would no longer be beneficial. In the second scenario, the patient develops advanced dementia. Each scenario has three response options: "The goals of care should focus on delaying my death, and thus I want to continue life-sustaining treatment", "The goals of care should focus on my comfort and peace, and thus I do not want life-sustaining treatment, including dialysis", and "I am not sure". Patients and surrogates complete this tool independently and their responses are then compared to determine dyad congruence -- either congruent in both scenarios or incongruent. If both members of the dyad endorse "I am not sure", they are considered incongruent.
- **Patient decisional conflict** will be measured using the 13-item Decisional Conflict Scale (DCS), a validated measure in the context of end-of-life decision making¹⁷; higher scores indicate greater difficulty in weighing benefits and burdens of life-sustaining treatments and decision making (range 1-5; Cronbach's $\alpha = 0.8 - .93^{17,18,20,72}$).

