 - 5) The proportion of decisions made at 6 months (e.g. stopping dialysis, DNR order, and hospice enrollment etc.) follow-up or death of patient will be higher in the intervention dyads than that of control dyads.
- Aim 2:
 - 1) HAD-anxiety scores in SPIRIT surrogates will be lower than those of control surrogates at 1 month after the patient's death.
 - 2) HAD-depression scores in SPIRIT surrogates will be lower than those of control surrogates at 1 months after the patient's death.

Supplement cohort study:

Aim 1. Changes in patient's goals of care preferences over time (T2-T3 and T2-T4) in the intervention group will be smaller than those in the control group.

Aim 2. Changes in the preparedness outcomes over time in the intervention group will be smaller than those in the control group.

Aim 3. The COVID-19 Related Stress and race/ethnicity will be significantly associated with changes in goals of care stability and the preparedness outcomes.

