Due to the exploratory nature of the study, a traditional sample size calculation was not performed. Instead, our goal was to provide estimates of effect sizes (standardized mean differences between pre- and during- COVID-19 study points) for the outcomes in aims 1-3. Preliminary power calculations based on a two-sample t-test, indicate that a sample size of 72 in the SPIRIT intervention and 35 in the usual care group achieve 80% power to detect a difference in mean changes of 0.5 between the groups. This calculation assumes a repeated measures design with a standard deviation of 1.0 at both time points, a between measurement correlation of 0.2 and a 5% significance level.

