Aim 1. Compare the stability of patients’ goals-of-care preferences over time, from pre-outbreak to during-outbreak, by group and estimate effect by race: We will use mixed effects modeling to assess differences in patients’ goals of care over time, from pre- to post-lockdown time points. We will sequentially build a longitudinal model that will include time, treatment group and race as fixed effects; then 2-way interactions of time x group, time x race, treatment x race, and finally a 3-way interaction of time x group x race, if the sample size permits. We will select the most parsimonious model using Akaike information criterion (AIC) and Bayesian information criterion (BIC). We will use contrasts to test whether participants demonstrated significant change in goals-of-care preferences across different combinations of treatment and race.

Aim 2. Assess the stability in the three preparedness outcomes, from pre-outbreak to during-outbreak by group, and estimate race effect: We will perform analyses similar to those described in Aim 1. In addition, for non-normal outcomes (binary, count) a generalized mixed effects model will be used. Appropriate contrasts will be used to assess differences in the outcomes over time by treatment groups, race and groups x race.

Aim 3. Examining the associations of the COVID-19 Related Stress, sex, race/ethnicity, and other sociodemographic characteristics to the level of changes in the preparedness outcomes and patient’s goals-of-care preference stability: We will use analysis of covariance to assess the relationship between COVID-19 related stress and changes in outcomes from T2 to T3 and T3 to T4, after controlling for the corresponding baseline values of the outcomes (i.e., T2 and T3 respectively). Using similar methods, we will evaluate whether there are disparate effects of sex, race/ethnicity and other sociodemographic factors on outcome changes and goals-of-care preference stability from T2 to T3 and T3 to T4, respectively

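### COVID-19 cohort Aim 1 asks whether individual patients keep their goals-of-care preference, but the planned contrasts estimate net shift by arm, so a null result cannot be read as equal stability

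*Combined protocol and SAP*

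**What the plan says.** The cohort study is described in several places.

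- **Aim.** Sections 1.1 and 9.4.2 state Aim 1 as comparing the stability of patients' "goals-of-care preferences over time, from pre-outbreak to during-outbreak, by group and estimate effect by race".
- **Hypothesis.** Section 9.1 expects that changes in a patient's "goals of care preferences over time (T2-T3 and T2-T4) in the intervention group will be smaller than those in the control group". No direction of change is given.
- **Outcome.** The Goals-of-Care Tool in section 8.1 has two scenarios. "Each scenario has three response options": continue life-sustaining treatment, comfort without it, or not sure. No coding of these answers for the Aim 1 model is given.
- **Analysis.** Section 9.4.2 says "We will use mixed effects modeling to assess differences in" patients' goals of care from before to after lockdown. It builds a "longitudinal model that will include time, treatment group and race as fixed effects", adds interactions, and then: "We will use contrasts to test whether participants demonstrated significant change in goals-of-care preferences across different combinations of treatment and race".
- **Sample size.** Section 9.2 gives "a sample size of 72 in the SPIRIT intervention and 35 in the usual care group" as achieving "80% power to detect a difference in mean changes of 0.5 between the groups".
- **Aim 3.** Section 9.4.2 names preference stability as something to relate to COVID-19 stress, sex, race/ethnicity and other sociodemographic factors. It does not define the term.

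**The concern.** Stability belongs to the individual: did this patient give the same answer later? The protocol reasons in those terms. Section 2.2 cites a review in which more than 70% of patients' preferences were stable, and asks whether a preference recorded before the pandemic can still be relied on. Section 4.2 posits that patients may discount what they said earlier, especially in the control group.

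Fixed-effect contrasts of time and group answer a different question: did the arms drift differently on average? A patient who moves from comfort to life-prolonging care and another who moves the opposite way both count as unstable, yet together they add nothing to the average. No section compares a per-patient measure of stability, or within-patient variability, between SPIRIT and control.

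The risk is in interpretation. A null time-by-group contrast could be reported as equally stable preferences, and as no protection from SPIRIT, when many more control patients had in fact changed their answers.

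**Working it through.** **The plan's own figure (section 9.2).** Inputs: 72 and 35 patients, difference in mean changes 0.5, SD 1.0 at both times, correlation 0.2, 5% level.

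- SD of change = √(2 × (1 − 0.2)) = 1.265.
- SE = 1.265 × √(1/72 + 1/35) = 1.265 × 0.2061 = 0.261.
- 0.5 / 0.261 = 1.92, so two-sided power = Φ(1.92 − 1.96) ≈ 48% (61% one-sided).

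The stated 80% is not reproduced. That is a separate matter and nothing below depends on it. What counts here is that the effect being powered is a difference in signed mean changes.

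**Illustration.** Treat the preference as binary and use two time points. Under an identity link the time-by-group contrast is then the difference between arms in mean signed change. Assume a share p of patients switch, with a fraction f of the switches going one way.

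- Mean change = (2f − 1)p.
- Variance of change = p − [(2f − 1)p]².

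Assumed rates are p = 0.30 in control (35 patients) and 0.10 in SPIRIT (72 patients). The 30% is the complement of the 70% figure in section 2.2. The 10% is purely an assumption. Tests are two-sided at 5%, with unequal variances and no clustering.

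- **Balanced (f = 0.5).** Expected difference 0, so rejection is about 5%.
- **75/25 split.** Difference = 0.5 × 0.20 = 0.10. SE = √(0.2775/35 + 0.0975/72) = 0.0963. z = 1.04, power ≈ 18%.
- **All one way.** Difference = 0.20. SE = √(0.21/35 + 0.09/72) = 0.0851. z = 2.35, power ≈ 65% (64% by simulation).
- **Proportion changed, any split.** Pooled p = (7.2 + 10.5)/107 = 0.165. Null SE = √(0.165 × 0.835 × 0.04246) = 0.0766. Power = Φ((0.20 − 1.96 × 0.0766)/0.0851) ≈ 72% (73% by simulation).

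**Other assumed rates, balanced switching, simulated:**

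| Control / SPIRIT switching | Mean-change test | Proportion-changed test |
|---|---|---|
| 30% / 20% | about 5% | about 22% |
| 30% / 5% | about 5% | about 94% |
| 40% / 10% | about 5% | about 95% |
| 50% / 20% | about 5% | about 89% |

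**A detail on variances.** A model with one common residual variance would not hold 5% exactly in the balanced 30%/10% case. The pooled variance is (71 × 0.10 + 34 × 0.30)/105 = 0.165, giving SE √(0.165 × 0.04246) = 0.0836. The true SE is √(0.30/35 + 0.10/72) = 0.0998. Rejection is 2 × [1 − Φ(1.96 × 0.0836/0.0998)] ≈ 10%. The true mean difference is still zero, so these rejections point either way equally often and do not measure stability.

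**The case against.** The strongest reply is that direction of change is part of the cohort's question. Section 2.2 asks whether a disaster makes seriously ill patients more or less likely to want aggressive treatment, and the background links fear to demand for such treatment. A shared shock with a theorised direction is what a time-by-group contrast can detect, and with one-way switching it loses little (64% against 73% above). This stands, and it is why the planned model should be kept.

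Two stronger readings are tempting, and the documents support neither.

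- A reader might infer that the cohort's main question goes untested. That is too strong. The contrast carries part of the information unless switching is balanced, and Aim 3 shows that the authors have a stability outcome in mind. What is missing is its definition and its comparison by arm.
- A reader might also infer that an arm with 20% switching each way (net 0.20 − 0.20 = 0, so 60% stable) gives the same model result as an arm in which nobody changes. Only the expected fixed effects match. Within-patient correlation, residual variance and standard errors would differ. The documents give no switch rates for this cohort, and nothing suggests 100% stability.

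It can also be said that the modelled variable is not fully specified, so it might already be a changed/unchanged indicator. This is unlikely. The model spans pre- and post-lockdown time points, an indicator of change from T2 has no value at T2, and section 9.2 works with mean changes.

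Finally, the cohort is exploratory, is labelled a non-clinical trial in section 3, and leaves the parent trial unaffected. That limits the weight of the point but does not remove it.

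**Conclusion.** The point holds in a limited form. The planned Aim 1 contrasts estimate net shift in preference by arm. The aim and hypothesis concern how many patients change, or how much, regardless of direction. The two agree only when switching is mostly one way. A null contrast therefore cannot be reported as equal stability.

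At 35 and 72 patients with assumed switching of 30% and 10%, the mean-change test rejects about 5%, 18% or 64% of the time as switching goes from balanced, to 75/25, to all one way. A test of the proportion changed rejects about 73% of the time in each case. These figures rest on assumed switch rates, a binary simplification of a three-option answer, and independent patients. They show how the loss depends on direction and are not a forecast for this cohort. The change is worth making because it is cheap. It does not bear on the parent trial's conclusions.

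**What to change.** In section 9.4.2, under the supplement cohort study:

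1. Define stability per patient as the same response as at T2, assessed at T3 and at T4, for each scenario and for both scenarios together. The both-scenarios rule parallels the match rule already used for dyad congruence in section 8.1.
2. State in advance how not-sure answers count: whether not sure at both times is stable, and whether a move from not sure to a firm choice is treated like a reversal.
3. Compare the indicator by arm with a logistic mixed model containing group, time (T3, T4), group-by-time and race as planned, with random effects for patient (two indicators each) and clinic cluster.
4. Report T2–T3 and T2–T4 transition tables by arm, so that direction and type of change are visible.
5. Use the same definition wherever Aim 3 refers to preference stability.
6. Keep the planned mixed model as a companion analysis of direction of change, state how the three options are coded for it, and say that a null contrast there is not evidence of equal stability.

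The cost is analysis-plan wording and some programming, with no new data collection. The downside is limited precision for small differences: about 22% power for 30% against 20% changing, before any loss from clustering. For an exploratory cohort meant to estimate effects, reporting the proportions with confidence intervals is adequate.

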6.3 MEASURES TO MINIMIZE BIAS: RANDOMIZATION AND BLINDING

Clinics covered by the same care provider who will deliver SPIRIT sessions will be combined to one cluster to avoid risk of contamination; this results in clusters (4 in GA, 3 in NC, 8 in NM, 5 in PA and 8 in VA). Because the numbers of available patients substantially vary across the clusters, to minimize group imbalance clusters will be stratified to three sizes: small (patient census ≤ 52), medium (53-105), and large (≥ 106). We will randomize clusters to either SPIRIT or usual care plus delayed SPIRIT, with randomly permuted blocks (sizes of 2 and 4) within cluster size stratum nested in each state, using a pseudo-random-number generator, by the Study Coordination Center.

Before the study starts, the Study Coordination Center will inform the group assignment for each cluster to the site PIs, with a unique ID consisting of abbreviations for state and cluster size stratum. While the heterogeneity in minority race/ethnicity across clusters improves the study's generalizability, stratification or pairing clusters by race/ethnicity is not feasible because some clinics uniquely serve one race with no comparable clinics within state. Group imbalances on race/ethnicity and other potential confounding factors will be examined and adjusted for in the analyses. The cluster randomized design prevents blinding patient-surrogate dyads and dialysis care providers to group allocation. However, research staff assessing effectiveness outcomes will be blind to group assignment.

For Supplement Aims:

[name] (biostatistician/Co-I) will generate a randomization scheme using stratified (by race), permuted block randomization with block size 5, using a random-number generator. Dyads will be randomized with equal allocation (1:1) to SPIRIT or usual care. Due to the nature of the intervention, blinding dyads to their group allocation is impossible, but the research staff assessing outcomes will be blind. Immediately after the completion of the baseline assessment by phone, the data collector will open a sealed envelope to identify group assignment and schedule an intervention session to take place ~ 2 weeks hence for SPIRIT as well as a follow-up data collection session in the next 2-3 days.

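### The COVID cohort compares arms assigned by clinic, yet its plan names no clinic term: random effects are unstated for Aims 1-2, and Aim 3 and the sizing ignore clustering

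*Combined protocol and SAP*

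**What the plan says.** Section 5.1 draws the cohort from parent-trial dyads who had finished baseline and the 2-week follow-up before 13 March 2020. Section 6.3 randomizes clusters of clinics, so arm is a cluster-level variable in the cohort too. The same section explains why clusters were not matched on race: "some clinics uniquely serve one race with no comparable clinics within state".

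The parent plan deals with clustering throughout. Section 9.2 allows for an ICC, 9.4.1 uses GEE and cluster-adjusted Cox models, and the opening of 9.4.2 has random effects for subjects and clusters.

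The cohort text in 9.4.2 is different. For Aim 1 it announces mixed effects modelling, then "We will sequentially build a longitudinal model that will include time, treatment group and race as fixed effects", followed by two-way and three-way interactions and selection by AIC and BIC. Aim 2 follows Aim 1. For Aim 3, "We will use analysis of covariance to assess the relationship between COVID-19 related stress and changes in outcomes", with similar methods for sex, race and other sociodemographic factors. The adjustment it promises is for patient characteristics. Section 9.2 describes "Preliminary power calculations based on a two-sample t-test" in which "a sample size of 72 in the SPIRIT intervention and 35 in the usual care group achieve 80% power". The target there is a between-arm contrast of 0.5 in mean change, and no ICC is given.

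**The concern.** A comparison of arms assigned by cluster has a variance that includes variation between clusters. If clinics differ in how much their dyads change from before to during the outbreak, an analysis that treats dyads as independent understates the standard error of the time-by-group contrast. Cohort Aims 1 and 2 rest on that contrast.

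Race raises a second issue. Where race differs between clinics, a race contrast partly compares clinics. It then shares the variance problem, and a clinic difference in change can also be read as a race difference. Section 9.1 predicts significant associations of race/ethnicity and COVID-related stress with change, so these results will be read as findings even though the cohort is exploratory.

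**Working it through.** **Inputs.** From 9.2 (cohort): 72 and 35 dyads, difference in mean change 0.5, "a repeated measures design with a standard deviation of 1.0 at both time points", "a between measurement correlation of 0.2 and a 5% significance level", stated power 80%. Sidedness is not given for the cohort; two-sided is assumed below. Number of clusters: 19 in the heading of the 9.2 power table, or 4 + 3 + 8 + 5 + 8 = 28 from the counts in 6.3. ICC: 0.01-0.04 in the 9.2 text, and up to 0.10 in its table for patient decisional conflict and surrogate confidence. These ICCs belong to parent outcomes. The ICC of change is not given, so 0.01-0.10 is an assumption.

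**The plan's own figure.** SD of change = √(1 + 1 − 2 × 0.2) = √1.6 = 1.265. Standard error = 1.265 × √(1/72 + 1/35) = 1.265 × 0.206 = 0.261. Power = Φ(0.5/0.261 − 1.96) = Φ(−0.04) ≈ 48% (also 48% with the t distribution). So the stated 80% is not reproduced as a two-sided test of mean change. That is a separate matter from clustering, and the point here does not depend on it.

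**Design effect with equal cluster sizes.** m = 107/19 = 5.63 or 107/28 = 3.82; DE = 1 + (m − 1) × ICC. The correct standard error is √DE times the naive one. The true error of a nominal 5% test is 2 × [1 − Φ(1.96/√DE)]. If 80% power is taken as given, it becomes Φ(2.80/√DE − 1.96).

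| Clusters | ICC of change (assumed) | DE | SE ratio | True error | Power, if 80% before |
|---|---|---|---|---|---|
| 19 | 0.01 | 1.046 | 1.023 | 5.5% | 78% |
| 19 | 0.04 | 1.185 | 1.089 | 7.2% | 73% |
| 19 | 0.10 | 1.463 | 1.210 | 10.5% | 64% |
| 28 | 0.01 | 1.028 | 1.014 | 5.3% | 79% |
| 28 | 0.04 | 1.113 | 1.055 | 6.3% | 76% |
| 28 | 0.10 | 1.282 | 1.132 | 8.4% | 70% |

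**Simulation of a t-test that ignores clinic (20,000 cohorts per setting).** With equal cluster sizes, 28 clusters give 6.0% (ICC 0.04) and 8.0% (ICC 0.10); 19 clusters give 6.7-7.6% and 9.6-10.5%, depending on how clusters divide between arms. With uneven sizes (shares drawn from a Dirichlet distribution with parameter 2), 28 clusters give 7.5% and 11.3%, and 19 give 8.7% and 13.6%. At ICC 0.01 a simulation gives 5.4-5.6%. The documents do not say how cohort dyads spread over clinics. Section 6.3 does say that patient numbers vary substantially across clusters, so equal sizes are the favourable case.

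**Race contrast.** The result depends on how strongly race is tied to clinic, which the documents do not quantify. With uneven clusters and an outcome ICC of 0.04, race unrelated to clinic gives 4.7-5.1%, and a clinic ICC of race of 0.2 gives 5.2-5.4%.

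**The case against.** **Aims 1-2 do not exclude a clinic term.** This is correct. The text lists only fixed effects and leaves out even a person effect, and the parent model in the same section has cluster effects. A reader might infer that the plan rules clinic out; it leaves clinic unstated. But nothing carries the parent term over: the cohort text invokes the parent study for data capture and missing data, not for the model. The Aim 3 analysis of covariance and the t-test sizing contain no clinic term as written.

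**A stable clinic effect cancels in change.** Also correct. Only clinic-by-time variation matters, and its size is unknown. A reader might infer that the standard errors are certainly too small. That does not follow; the inflation is conditional on a positive ICC of change. One might argue that the outbreak reached clinics at different times, but no document says so. Section 4.2 reports only that cases and deaths were concentrated in counties with larger Black populations. This makes differences between places plausible and does not measure them.

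**Race tests need not be inflated.** A reader might infer a general inflation of race tests. Section 6.3 speaks of some single-race clinics in the parent pool, not of the cohort dyads. Where race varies within clinics, ignoring clinic need not shrink the standard error.

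**The cohort is exploratory.** Section 9.2 says so and calls its calculation preliminary. This limits the weight of the point but is no reason to leave the model unspecified.

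**Conclusion.** The point holds as a gap in specification with a conditional consequence. Arm is a cluster-level variable, the parent plan treats it as one, and the cohort plan names no clinic term. For an arm test that ignores clinic, the true error at nominal 5% is about 5.5% at ICC 0.01, 6-9% at 0.04 and 8-14% at 0.10. With even clusters, the standard error is understated by a factor of 1.01 to 1.21.

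These figures assume that the ICC of change lies in the range that 9.2 gives for parent outcomes, that there are 19 or 28 clusters, and that dyads spread evenly or moderately unevenly. At the low end the effect is negligible; at 0.10 it is material. For race, the supportable statement is narrower: the contrast is affected, and confounded with clinic, to the extent that race differs between clinics. The parent primary analysis is not touched.

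**What to change.** In the cohort part of 9.4.2:

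- **Aims 1-2:** state that the mixed models include a person effect and a random cluster effect on change (cluster-by-time), and that AIC/BIC selection does not remove it.
- **Aim 3:** keep the same covariates, including the earlier value of the outcome, in a model with a random cluster intercept.
- **Inference:** use a small-cluster degrees-of-freedom correction. If the fit is singular, use cluster-robust errors with that correction.
- **Race:** report effects as possibly confounded with clinic, and add a within-clinic race contrast as a sensitivity analysis where clinics are mixed. Single-race clinics contribute nothing to that contrast.

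In 9.2, state that the cohort's 80% power ignores clustering.

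**Cost:** this is a change of wording and needs no new data collection, because clinic is part of the parent trial's design. Intervals will be somewhat wider. With about 4 to 6 dyads per cluster, convergence problems are possible, so the fallback should be written down in advance. A heavier model, with state fixed effects added to all of these terms, would be hard to support with about 107 dyads.

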- 4) Aim 3. Relationships among patients' cognitive status, decision-making capacity and their ability to express end-of-life wishes:** For patients in the SPIRIT intervention arm (n=15), associations between patients' cognitive status (continuous), decision-making capacity (continuous) and their ability to express end-of-life wishes (categorical) will be analyzed using one-way analysis of variance (ANOVA). We will also explore ordinal logistic regression to obtain the proportional odds ratios defined by the odds of "expressing wishes very coherently" or

“expressing wishes somewhat coherently” versus the odds of “unable to express wishes coherently” for a unit increase in cognitive status or decision-making capacity.

Supplement cohort study:

As in the parent R01, we will use the Research Electronic Data Capture (REDCap) to create and update study participants’ data. During data entry, automated checks will be performed that will immediately flag problematic data (e.g., missing, out of range, inconsistent). Preliminary analyses will include summarizing variables with descriptive statistics and graphical displays. We will assess distributional assumptions of the outcomes and apply appropriate transformations to remedy any violations. Any differences in patient characteristics (e.g. age, sex, education level, household income) across groups will be adjusted when modeling the outcomes. As observed in the parent R01 (< 1% missing data), we expect very little missing data. Nonetheless, we plan to use restricted maximum likelihood (REML) method for estimating the repeated measures analysis to minimize the impact of missing data. This will make it possible to retain cases with partial data while making less restrictive assumptions about missing data patterns.

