9.4.7 SUB-GROUP ANALYSES

In order to evaluate whether the SPIRIT has differential effects according to demographic factors such as age, sex, race/ethnicity we consider the same generalized mixed effects model in the context of protocol design, mentioned in Section 9.4.1. Our approach is first to consider each factor one at a time. We will fit the same generalized mixed model by additionally including a subject level factor (e.g., race) and its' interaction with the SPIRIT. If the interaction is significant the analysis will indicate that SPIRIT effect changes according to race. We will report p-values and importantly, standard errors and confidence intervals by recognizing the fact that we may not have power to detect significant interaction effects for examining all demographic factor combinations.

For Supplement Aims: no subgroup analyses will be possible due to the small sample size.

Supplement cohort study: no subgroup analyses will be possible due to the small sample size

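### In the supplement cohort study, the time-by-group term that carries the Aim 1 and Aim 2 hypotheses is an optional term in an AIC/BIC model search and can be selected out

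*Combined protocol and SAP*

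**What the plan says.** Section 9.1 gives the cohort's Aim 1 hypothesis as changes in "goals of care preferences over time (T2-T3 and T2-T4) in the intervention group will be smaller than those in the control group". Aim 2 says the same of the preparedness outcomes.

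Section 9.4.2 describes the Aim 1 model as a stepwise build that begins with main effects only: "We will sequentially build a longitudinal model that will include time, treatment group and race as fixed effects". The interactions, including the one that the hypotheses concern, enter at later steps: "then 2-way interactions of time x group, time x race, treatment x race, and finally a 3-way interaction of time x group x race", the last of these only if the sample size allows. A selection rule closes the build: "We will select the most parsimonious model using Akaike information criterion (AIC) and Bayesian information criterion (BIC"). Contrasts across treatment and race combinations follow. Aim 2 uses a similar analysis, with generalized mixed models for non-normal outcomes.

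On estimation, the same section says "we plan to use restricted maximum likelihood (REML) method for estimating the repeated measures analysis", giving missing data as the reason. No other estimator is named for the cohort's linear models, and the likelihood behind AIC and BIC is not stated.

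Section 9.2 calls the cohort exploratory, sets effect-size estimates as its goal, and bases its power statement on a difference in mean change between groups. Section 9.4.7 says: "Supplement cohort study: no subgroup analyses will be possible due to the small sample size".

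**The concern.** Both hypotheses compare change between arms, so the parameter of interest is time x group. The plan places that parameter in the optional part of a sequential build and then asks for the most parsimonious model. A model without it forces the same change in both arms, and no later contrast can recover the difference. If the term survives, its estimate and test are reported conditional on having survived, which favours large observed differences. Because no criterion governs when AIC and BIC disagree, the analyst could decide after seeing the data whether the hypothesis is tested.

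The estimator adds a second difficulty. REML likelihoods of models with different fixed effects are not comparable, because each contains a term in its own design matrix. The candidate models here differ in their fixed effects, and no ML fit is planned for comparing them.

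**Working it through.** **Inputs.** From section 9.2: 72 SPIRIT and 35 usual-care dyads, SD 1.0, correlation 0.2, difference in mean change 0.5, 5% level. Time points T2, T3 and T4 are from section 9.1. My assumptions: a Gaussian outcome, compound symmetry, and 0.5 at both T3 and T4.

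**1. The plan's own power figure, as a yardstick.**
- SD of a change = sqrt(2 x (1 - 0.2)) = 1.265.
- SE of the difference = 1.265 x sqrt(1/72 + 1/35) = 0.2606.
- Standardised effect = 0.5 / 0.2606 = 1.918.
- Two-sided power = Phi(1.918 - 1.960) = 48% (47.6% with the t distribution).

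The stated 80% does not reproduce. On these inputs, 80% needs a difference of 0.73. That is a separate matter; here it only means that the benchmark for any loss is about 50%, not 80%.

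**2. Probability of dropping time x group, one change (1 df).** Noncentrality = 1.918 squared = 3.68. The term is dropped if the deviance reduction is below the penalty.
- AIC, penalty 2: 31%.
- BIC, penalty ln(107) = 4.67: 60%. With n counted as 214 observations, ln(214) = 5.37: 66%.

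**3. The same with three time points (2 df).** The difference pattern (0, 0.5, 0.5) has sum of squares about its mean 1/9 + 1/36 + 1/36 = 1/6. Within-dyad variance is 1 - 0.2 = 0.8. Noncentrality = (1/6) / (0.8 x (1/72 + 1/35)) = 0.1667 / 0.0340 = 4.91.
- Pre-specified joint test, cutoff 5.99: power 50%.
- AIC, penalty 4: dropped in 32%.
- BIC, penalty 2 x ln(107) = 9.35: dropped in 74%. With n = 321 observations, penalty 11.54: 84%.
- AIC keeps the term and BIC drops it in 74 - 32 = 42%.

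**4. What dropping costs in detections.** The AIC penalty (4) lies below the 5% cutoff (5.99), so ML-AIC cannot drop a term whose joint test is significant. The BIC penalty (9.35) lies above the cutoff, so significant terms with a deviance reduction between 5.99 and 9.35 are lost: about 50% power falls to 100 - 74 = 26%, a loss of about 24 points.

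**5. Simulation with the same inputs (runs of 400 to 1,000 data sets).** ML-AIC kept the term in 69-70% and ML-BIC in 29%. The pre-specified joint test was significant in 51-52%. ML-AIC dropped no data set with a significant joint test; ML-BIC lost 23-24 points. AIC and BIC disagreed under ML in 40%. Running the whole sequence of candidate models, with an assumed 60% in one race group, gave drop rates of 31% (ML-AIC) and 75-84% (ML-BIC, n as dyads or observations).

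**6. If the criteria came from REML fits.** In one simulated three-time-point data set, the two time x group columns were multiplied by a constant c, which leaves the model unchanged. The ML deviance difference stayed at 5.206. The REML difference moves by 2 x 2 x ln(c):

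| c | REML deviance difference | AIC decision (penalty 4) |
|---|---|---|
| 0.5 | 5.68 | keep |
| 1 | 2.91 | drop |
| 2 | 0.14 | drop |
| 10 | -6.30 | drop |

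Across simulated data sets, REML-AIC kept the term in 51-53% with 0/1 arm coding and 31-32% with -1/+1 coding. The decision changed with coding alone in 21%.

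**The case against.** Four points deserve weight.

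- *The plan may intend to keep the term.* Aim 2 commits to contrasts of change by treatment group, which presuppose the interaction, and the sample-size condition most naturally attaches only to the three-way term. This shows the text is ambiguous. It does not protect the term, because the selection rule covers the whole build and exempts nothing.
- *A reader might infer that the plan takes AIC/BIC from REML fits.* It does not say so. Comparing ML fits and then refitting by REML is compatible with both sentences. The REML difficulty is therefore conditional. It clearly reaches only decisional conflict and decision-making confidence: dyad congruence is binary, and the goals-of-care responses are three categories. The Gaussian calculation does not represent those outcomes.
- *A reader might treat the drop rates as lost detections.* They are not. ML-AIC loses no significant joint test. The real loss of power comes with BIC, and still higher drop rates need REML, BIC and a particular coding together, a combination the plan does not specify. What ML-AIC does cost, in about 30% of data sets, is the between-arm estimate.
- *A reader might say the race contrasts flatly contradict section 9.4.7.* Estimating effects by race is a declared cohort aim in the synopsis, and the three-way term is hedged. The contrasts across treatment and race combinations are not hedged, so the sections are in tension and need reconciling.

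Nor does any section say that a dropped term would be reported as no difference in stability.

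**Conclusion.** The point holds for the selection rule. As written, it can remove the parameter that both hypotheses are about, and nothing settles a disagreement between AIC and BIC. That is more than a missing detail, because the cohort's stated purpose is to estimate effects. The size depends on the criterion: about 30% removal without loss of significant joint tests under ML-AIC, and about 71% removal with a loss of 23-24 points from roughly 51-52% power under ML-BIC. These figures rest on section 9.2's inputs, a Gaussian outcome, compound symmetry, and a difference of 0.5 at both follow-ups. The REML part stands only conditionally and for the two continuous scales. The change is worth making but not critical: the cohort is exploratory, and the parent trial's endpoints are untouched.

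**What to change.** In section 9.4.2, for cohort Aims 1 and 2:

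- Keep time, group, race and time x group in the model regardless of AIC/BIC, and test the hypotheses with the T3-T2 and T4-T2 time x group contrasts.
- Limit selection to the race interactions, and name one governing criterion. If it is BIC, say whether n counts dyads or observations.
- Compute that criterion from ML fits, and refit the final continuous-outcome model by REML.
- Report any race-specific contrasts as estimates with intervals, and reconcile them with section 9.4.7.

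This costs wording only; no data collection or sample size changes. It brings the risk of removing the hypothesis term to zero and leaves its test at the nominal level with the design's own power.
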